4.2 Phase 2: Food Introduction

4.2.1 Visit 5, 9, 13

1 week (+/- 3 days) after visit 4, 8 and 12

- EoE Symptom Score-PEESS and PESQ (SOC procedure)
- Drug disposition
- New food introduction
- Monitor drug compliance
- AE assessment
- Physical Examination including vital signs with height and weight

4.2.2 Visit 6, 10, 14

2 weeks (+/- 4 days) after preceding visit. This visit can be done by remote research visit.

- EoE Symptom Score-PEESS and PESQ (SOC procedure)
- Drug disposition
- Review food diary
- Monitor drug compliance
- AE assessment
- Physical Examination including vital signs with height and weight

4.2.3 Visit 7, 11, 15

5 weeks (+/- 4 days) after preceding visit. This visit can be done by remote research visit.

- EoE Symptom Score-PEESS and PESQ (SOC procedure)
- Review food diary
- Monitor drug compliance
- AE assessment

4.2.4 Visit 8, 12, 16

- Upper Endoscopy with biopsy-4 esophageal biopsies (SOC procedure)
- EoE Symptom Score-PEESS and PESQ
- EoE QOL
- Review food diary
- Drug disposition (except for visit 16)
- Monitor drug compliance

- AE assessment
- Physical Examination including vital signs with height and weight
- Endoflip and/or esophageal impedance
- Research bloods: (T cell phenotype, PBMC RNAseq, peripheral blood eosinophils and progenitors, proteomics)-15 ml of blood
- Research Biopsies: Esophageal biopsy RNAseq-6 esophageal biopsies
- AE assessment

4.3 Follow-up Phase

4.3.1 Visit 17: End of Study

- AE assessment
- Physical Examination including vital signs with height and weight

4.4 Unscheduled Visits

All attempts should be made to keep patients on the study schedule. Unscheduled visits may be necessary to repeat testing following abnormal laboratory results, for follow-up of AEs, or for any other reasons as warranted.

4.5 Concomitant Medication

All prior and concomitant medications used within 14 days prior to the screening visit and through the end of the study will be recorded. The dates of administration, dosage, and reason for use will be included.

4.6 Subject Completion/Withdrawal

Subjects may withdraw from the study at any time without prejudice to their care. They may also be discontinued from the study at the discretion of the Investigator for lack of adherence to study treatment or visit schedules, AEs, or due to lack of response to dupilumab as defined by esophageal biopsy greater than 15 eosinophils/high power field at week 12. The Investigator may also withdraw subjects who violate the study plan, or to protect the subject for reasons of safety or for administrative reasons. It will be documented whether or not each subject completes the clinical study. If the Investigator becomes aware of any serious, related adverse events after the subject completes or withdraws from the study, they will be recorded in the source documents and on the CRF.

4.6.1 Early Termination Study Visit

Subjects who withdraw from the study will have all procedures enumerated for Visit 8 as the early termination visit.

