Visit Number	1	2	3	4	5	6*	7*	8	9	10*	11*	12	13	14*	15*	16	17
Study weeks	1	3	8	12	13	15	20	25	26	28	33	38	39	41	46	51	52
Informed Consent/Assent	X																
Review Inclusion/Exclusion Criteria	X																
Demographics/Medical History	X																
Physical Examination	X	X	X	X	X	X		X	X	X		X	X	X		X	X
Vital Signs: BP, HR, RR	X	X	X	X	X	X		X	X	X		X	X	X		X	
Height and Weight	X	X	X	X	X	X		X	X	X		X	X	X		X	
EGD and biopsy				X				X ^a				X ^a				X ^a	
EREFs				X				X ^b				X ^b				X ^b	
EoE Symptom Score	X	X	X	X	X ^b	X ^b	X ^b	X ^b	X ^b	X ^b	X ^b	X ^b	X ^b	X ^b	X ^b	X	
EoE QOL	X			X				X				X					X
Food Introduction [#]				X				X				X					
Pregnancy Test	X																
Prior/Concomitant Medications	X																
Research laboratory	X			X				X				X				X	
CBC (safety)	X			X				X				X				X	

T cell phenotype, PBMC RNAseq	X			X				X				X				X	
Dispense Study Drug	X	X	X	X	X	X		X	X	X		X	X	X			
Drug Compliance		X	X	X	X	X		X	X	X		X	X	X		X	
Adverse Event Assessment		X	X	X	X	X	X	X	X	X	X	X	X	X	X	X	X

ERFS-EoE Endoscopy Reference Score

EoE QOL-Eosinophilic Esophagitis Quality of Life measure

*Visits can be done via remote research visit

a-EGDs are standard of care biopsies for food introduction

b-SOC procedures

Food Introduction

Foods in phase 1 will be introduced as one serving size at week 13. If biopsy at week 25 are less than 6 eosinophils/HPF, the subjects will have one of 2 options

- Increase the serving size to 2 servings a day or
- Add an additional EoE trigger food

If the week 25 biopsy show 6-15 eosinophils/hpf, the diet will remain the same

If the week 25 biopsy show >15 eosinophils, the diet will decrease to ½ serving size a day

[figure not shown]
For the week 38 endoscopy with biopsy, the three scenarios are

If the biopsy show < 6 eosinophils/hpf, the three options are

- Increase the serving size to ad lib (if one food) or
- Add a 3rd EoE trigger food or
- Increase the serving size of 1st and 2nd foods to 2 serving size a day

If the biopsy shows 6-15 eosinophils/hpf, the plan is to remain at the current diet

If the biopsy show >15 eosinophils/hpf, the plan is to decrease the serving size by 50%

FIGURE 1: STUDY DIAGRAM

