3 INVESTIGATIONAL PLAN

3.1 General Schema of Study Design

This study is an open label exploratory study to examine if patients controlled with dupilumab can successfully introduce EoE trigger foods back into their diet.

In the initial 12-week period, patients will start on dupilumab on the doses used in the phase 3 trials to control disease. If disease is controlled based on histologic and symptom control at week 12 endoscopy, patients will start on EoE trigger food. The trigger foods will be based on both a combination of history and histology results. The food will have triggered EoE by histology in the last 2 years and symptoms in the last year when reintroduced into the diet. The study will focus on the four most common foods that trigger EoE: milk, egg, wheat, and soy. For the initial food introduction, the subjects will add one serving size of the food daily for 12 weeks. After 12 weeks, the subjects will have a 2nd endoscopy if the 2nd endoscopy is normal, the subjects will increase the trigger food to 2 serving sizes a day or add an additional trigger food. A 3rd endoscopy will be done if the patients increase the food amount or adds a new food at week 38 (12 weeks after adding the new food). If the subject does not increase or add new foods at week 25, the 3rd endoscopy will not be obtained. All subjects will have end of study endoscopy at week 51.

If the subjects have abnormal endoscopy or increase in symptoms, the amount of food will be reduced by 50% and repeat endoscopy will be obtained at the same time schedule-12 weeks later. (See Figure 1 and Table 1)

Screening Phase

Potential subjects will be screened using the protocol inclusion and exclusion criteria based on review of their medical records.

Parental/guardian permission (informed consent) and, if applicable, child assent, will be obtained prior to any study related procedures being performed. After consent is obtained, research blood samples will be drawn to confirm eligibility based on clinical laboratory parameters. Females of child bearing potential will have an urine pregnancy test.

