3.4.4 Individual stopping rules

Subjects may withdraw from the study/schedule of assessments for any of the following reasons:

- Patients will be stopped if they have severe adverse reaction from a serious adverse event from injection reaction
- The Investigator decides that it is the subject's best interest to be withdrawn from the study.
- The subject is unwilling to continue in the study (consent withdrawal).
- Lack of compliance with protocol requirements and procedures.
- The Sponsor- Investigator or Regulatory Authorities, for any reason, stops the study.
- The subject fails to return to the clinic for scheduled visits and does not respond to telephone or written attempts at contact (lost to follow-up).
- Subject's death

The reason for withdrawal will be recorded in the clinical records and the electronic Case Report Form (eCRF). All subjects who are withdrawn or discontinue should be provided with alternative medical care, if applicable.

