In the 52-week phase 3 clinical trial for EoE, 81 pts were randomized in Part A 1:1 to dupilumab (42) or placebo(39) for 24 weeks; 77 pts continued into Part C to dupilumab for a further 28 weeks (40 from dupilumab/dupilumab, 37 from placebo/placebo). The most common treatment-emergent adverse events for dupilumab/dupilumab arm and placebo/dupilumab arm were injection-site reactions (10.0% and 21.6%) and injection site erythema (10.0% and 13.5%). In part B of the phase 3 clinical trial, patients were randomized 1:1:1 to placebo, q weekly or q2 weekly dosing with 115 patients in each arm. There were no significant differences in adverse event rates. The overall rates of treatment-emergent adverse events were similar for dupilumab/placebo (83.8%/70.5%), the most common being injection-site reactions (MedDRA High-Level Term, 37.5%/33.3%).^{11, 12}

The dosing from the 52 weeks clinical trial for EoE showed no novel adverse events compared to the adverse event for asthma or atopic dermatitis. There were lower rates of conjunctivitis in the EoE clinical trial compared to the atopic dermatitis clinical trial and similar rate to the asthma clinical trial.

To summarize, the most common risks that have identified in pediatric trials of dupilumab are injection site reaction, and conjunctivitis and there are no significant differences between Qweek and Q2week dosing.

It is also not predicted to be any difference in adverse events between patients 6-12 with asthma, atopic dermatitis or EoE based on

- 1) No difference was detected in subjects > 12 years of age in published phase 3 trials in asthma, atopic dermatitis and EoE
- 2) No difference in adverse events was seen in our patients > 6 years of age treated for asthma or atopic dermatitis with or without Eosinophilic Esophagitis
- 3) There are no biologic reasons to predict an increased risk of adverse events in patients with EoE at any age.

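### Section 4.6.1 sends leavers to Visit 8, whose list includes dispensing dupilumab; it should point to Visit 16 and spare a repeat endoscopy before any trigger food

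*Combined protocol and SAP*

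**What the plan says.** The early termination rule (4.6.1) is one sentence: "Subjects who withdraw from the study will have all procedures enumerated for Visit 8 as the early termination visit". It makes no distinction by reason for leaving or by study phase.

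Visit 8 shares a list with Visits 12 and 16 in 4.2.4. That list includes an endoscopy with 4 clinical biopsies, "Research Biopsies: Esophageal biopsy RNAseq-6 esophageal biopsies", Endoflip and/or impedance, 15 ml of research blood, and "Drug disposition (except for visit 16"). Table 1 has a row headed "Dispense Study Drug", which is marked at Visit 8 and blank at Visit 16.

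The routes out of the study are set out elsewhere:
- 3.4.4 lists reasons for withdrawal. The first is: "Patients will be stopped if they have severe adverse reaction from a serious adverse event from injection reaction". Consent withdrawal is also listed.
- 4.6 adds discontinuation at the investigator's discretion, including for non-response at week 12.
- 3.1.1 and 3.3.1 say that week-12 non-responders exit.
- 5.1.11 says that a subject who becomes pregnant stops dupilumab at once and is not followed.

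None of these sections mentions the termination visit, and no other exit visit is defined.

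**The concern.** A termination visit should collect final data and recover drug. Visit 8 falls in mid-treatment, with dosing continuing to week 51, so its list contains things a leaver should not receive.

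The first is study drug. A subject stopped for a severe reaction to the injection is the clearest case: 3.4.4 stops the drug, and 4.6.1 as worded supplies more of it.

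The second is an endoscopy whose stated justification may be missing. Section 7.10.2.2 regards only the first endoscopy as research and the later ones as standard of care because they follow food introduction. The risk assessment in 7.10.2.1 is written for a single research endoscopy. A subject who had the Visit 4 endoscopy, ate no trigger food and then left would have a second sedated procedure, with 6 research biopsies, that this reasoning does not cover.

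What is at stake is safety and burden in a study that enrolls from age 6. No statistical result depends on it.

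**Working it through.** **Does the disposition item mean dispensing?** Set the visit lists in 4.1 and 4.2 beside Table 1.

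| Source | Visits |
|---|---|
| Drug disposition, 4.1 and 4.2 | 2–6, 8–10, 12–14 |
| Dispensing row, Table 1 | 1–6, 8–10, 12–14 |

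The only difference is Visit 1, where 4.1.1 gives the first dose. The item is also waived at Visit 16, where treatment ends and a drug return would matter most, while compliance monitoring is a separate item that stays at Visit 16. So the item is dispensing, and Visit 8 includes it.

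**Which endoscopies does the plan justify by food?** Table 1 (footnote a) and 7.10.2.2 call the endoscopies at Visits 8, 12 and 16 standard of care for food introduction. The Visit 4 endoscopy is the research one. A leaver between Visit 4 and the first food has had the research endoscopy and has no food introduction to justify another. Under 4.6.1 the second would take 4 + 6 = 10 biopsies. A subject who leaves before Visit 4 is a different case: the termination endoscopy would be their first.

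**How many leavers?** The plan gives no dropout assumption. The nearest figure is in 7.10.2.4: "81 pts were randomized in Part A 1:1 to dupilumab (42) or placebo(39) for 24 weeks", then "77 pts continued into Part C to dupilumab for a further 28 weeks (40 from dupilumab/dupilumab, 37 from placebo/placebo"). Assume that the dupilumab subjects who did not continue are withdrawals:
- 42 − 40 = 2, and 2/42 = 4.76% over 24 weeks. The exact (Clopper-Pearson) 95% interval is 0.58% to 16.16%.
- Of 30 subjects: 30 × 0.0476 = 1.4 over 24 weeks (interval 0.17 to 4.85).

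Carry the same constant rate to week 51, with the 19 evaluable subjects of 5.6 continuing after week 12:
- Weeks 0–12: 30 × (1 − 0.9524^(12/24)) = 30 × 0.0241 = 0.72.
- Weeks 12–51: 19 × (1 − 0.9524^(39/24)) = 19 × 0.0762 = 1.45.
- Total: 0.72 + 1.45 = 2.2.

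This gives about 1 to 2 leavers.

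**How many leave after Visit 4 but before any food?** For most subjects only the week between Visits 4 and 5 is exposed: 30 × (1 − 0.9524^(1/24)) = 30 × 0.00203 = 0.06. Subjects at 6–15 eos/hpf are exposed for 12 weeks more (3.1.1), and the documents do not say how many there will be. Even if all 30 were extended, the figure is 30 × (1 − 0.9524^(13/24)) = 0.78. At this rate the group is below one subject.

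**Are week-12 non-responders covered?** Section 4.6.1 applies to those who withdraw. Section 4.6 calls non-responders discontinued, 3.1.1 and 3.3.1 say they exit, and 3.4.4 does not list non-response. Yet 4.6.1 excludes nobody and there is no other exit visit. If it does apply, they would repeat the Visit 4 endoscopy about a week later (exit at week 13). The text leaves this open.

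**The case against.** The strongest reply is that nobody would act on the literal wording. Section 3.4.4 stops the drug, 5.1.11 stops it in pregnancy and ends follow-up, and 6.1.3 already requires unused drug back at each visit. Section 6.1.4 also uses disposition broadly, for receipt, dispensing, return and destruction. Withdrawal is voluntary, so no leaver can be made to have an endoscopy. Much of this stands and is why the point is minor. It does not remove it: the visit-by-visit match with Table 1 settles the meaning of the item, and a written safety rule should not rely on staff ignoring it.

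Three stronger readings are tempting, and the documents do not support them.

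- *Leavers would be told to start a new food.* Table 1 marks food introduction at Visit 8, but 4.2.1 places it at Visits 5, 9 and 13, and the 4.2.4 list does not contain it. That is a separate discrepancy.
- *Many non-responders face a repeat endoscopy.* Coverage by 4.6.1 is only arguable, and Visit 4 has already given these subjects the endoscopy, biopsies and blood. The site's series (1.3.1.1, 1.5) reports counts below 6 or normalization, not counts above 15. Subtracting the 59.5% below 6 in 5.6 from the 64% below 15 in 1.3.1.1 does not estimate the 6–15 group, because the two figures come from different sources.
- *The termination endoscopy should be limited to subjects whose food changed since their last one.* Section 3.1 does say "If the subject does not increase or add new foods at week 25, the 3rd endoscopy will not be obtained", which looks like a precedent. But it goes straight on to plan an end-of-study endoscopy for everyone at week 51, and the maintenance endpoints in 5.3.2 use that histology. Such a limit would be a trade-off, not a correction.

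Section 5.1.6 allows up to six endoscopies against four scheduled. That leaves room for an extra one but does not justify it.

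**Conclusion.** The point holds as a minor correction. That 4.6.1, read literally, has drug dispensed to leavers is well supported by the text. That 7.10.2.2 does not justify a second endoscopy before any food is also supported, but it probably concerns nobody unless week-12 non-responders are included. Whether they are, and how many, cannot be determined from the documents.

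The size, about 1 to 2 of 30, rests on treating 2 of 42 phase 3 subjects as withdrawals, which the protocol does not state, and on a constant rate beyond 24 weeks. The interval is wide (0.17 to 4.85 of 30 over 24 weeks). Sample size, alpha and the primary analysis are untouched.

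**What to change.** 1. In 4.6.1 replace Visit 8 with Visit 16, citing the list in 4.2.4, where dispensing is already waived.
2. State that 3.4.4 and 5.1.11 override 4.6.1.
3. Add one sentence: subjects who exit for non-response after the week-12 endoscopy, or who leave after a study endoscopy without having started any trigger food, do not repeat the endoscopy and research biopsies; their last study endoscopy serves as the termination endoscopy.
4. Keep the termination endoscopy, if the subject agrees, for anyone who has started a trigger food, even on a diet unchanged since the last endoscopy. This matches the end-of-study endoscopy that 3.1 plans for all.

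The cost is two or three protocol sentences, which only remove procedures. The downside is that leavers who never started a food contribute no extra biopsy. They have no post-food value for the primary endpoint in any case.

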5 STUDY EVALUATIONS AND MEASUREMENTS

5.1 Screening and Monitoring Evaluations and Measurements

5.1.1 Medical Record Review

Prior to screening visit, previous upper endoscopy and biopsy results and diet history will be reviewed. This information will be collected as part of routine clinical care.

5.1.2 Medical History

Complete medical history will include history and duration of all allergies (including milk, Egg, soy, or wheat allergy) and current medical conditions, number of allergic reactions and treatments in the previous 12 months, past or present cardiovascular, respiratory, gastrointestinal, renal, hepatic, neurological, endocrine, lymphatic, hematologic, immunologic, dermatological, psychiatric, and genitourinary disorders, drug and surgical history and any other diseases or disorders.

5.1.3 Physical Examination

Physical examinations will be performed by a physician or nurse practitioner and will include examination of the following: general appearance, head, ears, eyes, nose and throat, neck, complete skin examination, cardiovascular system, respiratory system, abdominal system, and nervous system. For each body system an assessment of normal or abnormal will be recorded in the eCRF at screening and the abnormality will be documented. During the study, any clinically relevant changes observed during physical examinations will be reported as AEs.

Physical examinations must be performed before the upper endoscopy/biopsy.

5.1.4 Vital Signs

Vital signs will include sitting systolic and diastolic blood pressure, heart rate, respiratory rate, and temperature. Systolic blood pressure and diastolic blood pressure will be measured on the same arm after the subject has been in a sitting position for 5 minutes. Heart rate will be recorded simultaneously with blood pressure measurements, followed by respiratory rate and body temperature.

Body weight (kg) will be measured without shoes or jacket. Height (cm) will be determined at without shoes.

During the study, the measurement of vital signs may be repeated at the discretion of the Investigator for safety reasons. Clinically relevant abnormal findings will be reported as AEs.

Vital signs must be performed before the upper endoscopy/biopsy.

5.1.5 Eosinophilic Esophagitis Quality of Life

Quality of life is a measurement of a subject's overall well-being. QOL will be measured by the validated age specific Eosinophilic Esophagitis tool for 5-7 years of age, 8-12 years of age, and 13-18 years of age developed by Franciosi and colleagues based on the age of the subject at Visit 1.

The subjects will complete the same questionnaire throughout the study.

5.1.6 Upper Endoscopy with Biopsy

All subjects will undergo a maximum of six upper endoscopies with biopsies during their participation in the study (biopsies will include three each of proximal and distal, plus any inflamed areas) as per standard clinical practice). The samples will be processed by the Department of Pathology at The Children's Hospital of Philadelphia and the number of eosinophils will be counted using hematoxylin and eosin stain. The handling of samples will be done following ASGE Standard on Endoscopic Mucosal Tissue Sampling.²⁸

Six research biopsies will be obtained in addition to the clinical biopsies. The biopsies will be taken from other areas of the esophagus compared to the clinical biopsies.

Upper endoscopy will be scored using a validated standardized measure.²² The measure examines four major esophageal features (rings, furrows, exudates, and edema) and the presence of minor features of narrow caliber esophagus, feline esophagus, stricture, and crepe paper esophagus. The features are graded:

- Rings (0-none, 1-mild, 2-moderate, 3-severe)
- Exudates (0-none, 1-mild, 2-severe)
- Furrows- (0-none, 1-present)
- Edema- (0-none, 1-present)
- Stricture (0-none, 1-present)
- Crepe paper esophagus (0-none, 1-present)

Endoscopy and biopsy are standard of care after food introduction.

The endoscopy will be done under moderate conscious sedation. Moderate sedation is defined as a drug-induced depression of consciousness during which patients respond purposefully to verbal command that is accompanied by light tactile stimulation. No interventions are required to maintain a patent airway and spontaneous ventilation is adequate. Cardiovascular function is usually maintained.

Conscious sedation will be done by CHOP standard protocol: Policy: Protocol Sedation:
<http://intranet.chop.edu/patcare/patcarman/tx-5-01.pdf>

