3.1.2 Food Introduction

If research subjects have a clinical response to dupilumab, they will introduce an EoE trigger food at one serving size per day. After 12 weeks, repeat EGD and symptoms score will be obtained. 12 weeks is being used as determined clinical and histologic responses can be seen at that time point in previous clinical studies¹⁸.

The foods (milk, egg, soy, and wheat) to be introduced after having caused exacerbation of their EoE by standard definitions:

- Addition of a single food lead to exacerbation of esophageal eosinophilia (increase of greater than 15 eos/hpf) or
- Removal of a single food lead to normalization of biopsy (esophageal eosinophilia showed less than 6 eos/hpf)
- AND
- History of either milk, egg, soy, or wheat induced EoE based on introduction of the food and symptoms in the last 12 months

Foods in phase 1 will be introduced as one serving size at week 13. If biopsy at week 25 are less than 6 eosinophils/HPF, the subjects will have one of 2 options

- Increase the serving size to 2 servings a day or
- Add an additional EoE trigger food

If the week 25 biopsy show 6-15 eosinophils/hpf, the diet will remain the same

If the week 25 biopsy show >15 eosinophils, the diet will decrease to ½ serving size a day

For the week 38 endoscopy with biopsy, the three scenarios are

If the biopsy show < 6 eosinophils/hpf, the three options are

- Increase the serving size to ad lib (if one food) or
- Add a 3rd EoE trigger food or
- Increase the serving size of 1st and 2nd foods to 2 serving size a day

If the biopsy shows 6-15 eosinophils/hpf, the plan is to remain at the current diet

If the biopsy show >15 eosinophils/hpf, the plan is to decrease the serving size by 50%

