3.2 Allocation to Treatment Groups and Blinding

All patients will receive active drug.

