5.1.7 Histological Evaluation

Esophageal biopsy samples will be evaluated to confirm eligibility. Biopsy samples will be stained with hematoxylin and eosin stain. Intraepithelial eosinophils will be counted in all HPFs using 400X light microscopy. A HPF will be counted only if at least half of the field is occupied by tissue. The maximum eosinophil count per HPF will be reported for each esophageal biopsy site (at each

of 2 levels) with a minimum of 2 biopsies at each level. In addition to the evaluation for eosinophilia, all biopsy samples will be assessed for other histologic changes including epithelial hyperplasia, intercellular edema, and fibrosis.

Specimens will be examined with respect to the maximum eosinophil counts and other histologic changes. Together with the EoE Clinical Symptom Score, the maximum eosinophil count per HPF for each specimen (from the total of all specimens) will be used to determine response to treatment.

The maximum eosinophil count will be defined as the highest number of eosinophils observed in any single HPF from an esophageal specimen. All specimens from all esophageal sites will be considered in determining the resolution of eosinophilia. A maximum eosinophil count will be recorded for the esophagus. The highest peak counts at a given timepoint will be referred to as the maximum eosinophil count for that timepoint.

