5.1.12 Research Laboratory Tests

The differential gene expression profiles of esophageal biopsies of EoE patients show a marked difference compared to healthy controls and is the EoE disease transcriptome³². This disease gene expression signature was further refined to a smaller gene set to be used as an EoE diagnostic panel (EDP)³³. A gene signature representing type 2 inflammation has been curated from the literature, preclinical experiments performed at Regeneron, and dupilumab response signatures from atopic dermatitis and a phase 2 and 3 study of EoE (Regeneron unpublished data).

In a phase 2 study of EoE (R668-EE-1324), dupilumab significantly decreased the disease, EDP, and type 2 transcriptome signatures. Normalized Enrichment Score (NES) reflects the degree to which the activity level of a set of transcripts is overrepresented at the extremes (top or bottom) of the entire ranked list of transcripts within a sample and is normalized by accounting for the number of transcripts in the set^{34, 35}.

The research bloods that will be collected include:

T cell phenotyping for T1/T2/Th17 expression, blood eosinophilia (CBC) and eosinophilic progenitor cells measured by flow cytometry in peripheral blood.

We will collect patient 6 biopsies and 15 ml peripheral blood at the time of study endoscopy. Patient samples will be provided to laboratory and CAG staff using the deidentified study code. Biopsy tissue will be dissociated in media containing RNase inhibitors and single cell RNA expression libraries will be generated following 10x genomics manufacturer protocols. Peripheral blood mononuclear cell samples will be isolated from patient blood samples and single cell RNA expression libraries will be generated following 10x genomics manufacturer protocols. Single cell RNA libraries will be pooled and sequenced to a minimum depth of 20,000 reads per cell using next generation sequencing (Illumina) at CHOP Center for Applied Genomics (CAG).

Patient sequencing data will be stored using deidentified study codes and will not be associated with patient names or any protected health information. Sequencing data will be transferred

from the CAG to study staff for analysis and stored using CHOP IT managed laboratory data drives (i.e.: <SMB://ressmb>). Sequencing data will not be stored on personal devices. Data analysis will be performed on CHOP managed devices and on the CHOP high performance computing cluster.

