5.3 STATISTICAL CONSIDERATIONS

5.3.1 Primary Endpoint

The primary efficacy endpoint will be the change in peak eosinophil counts on esophageal biopsies between 1st and 2nd endoscopy after food introduction in the same patient.

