7.7.3 Blinding

Not applicable, all patients are receiving active therapy

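### Cheap improvement: the plan does not say that the pathologist who reads the primary eosinophil count is masked to visit and food step

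*Combined protocol and SAP*

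**What the plan says.** The primary endpoint (section 5.3.1) is the "change in peak eosinophil counts on esophageal biopsies between 1st and 2nd endoscopy after food introduction in the same patient". Section 3.1 states the design: "This study is an open label exploratory study". Section 3.2 adds: "All patients will receive active drug".

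Reading of the slides is covered in two places:
- Section 5.1.6 assigns the samples to the hospital's pathology department, where "the number of eosinophils will be counted using hematoxylin and eosin stain".
- Section 5.1.7 sets the rule: "Intraepithelial eosinophils will be counted in all HPFs using 400X light microscopy". A field must be at least half tissue to count, at least two biopsies are read at each of two levels, all specimens are considered, and the highest single-field count is the value for that time point.

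Neither section mentions masking of the reader. The only entry on blinding, section 7.7.3, reads "Not applicable, all patients are receiving active therapy". It stands in the part of section 7.7 that deals with treatment assignment, next to randomization.

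The count is also used while the trial runs. Section 3.1.2 sets the next diet step from three bands (<6, 6-15, >15) at weeks 25 and 38, for example "If the week 25 biopsy show >15 eosinophils, the diet will decrease to ½ serving size a day". Section 5.3.2 uses <6 and <15 as secondary endpoints.

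**The concern.** The reason given for no blinding, that everyone receives active drug, explains why treatment is open. It does not settle whether the outcome should be read without knowledge of time point and diet. Both vary within each patient, so a reader can be masked to them in a single-arm trial.

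The endpoint is a maximum, so one field fixes the value. If a reader who knows that trigger food has been added classifies borderline cells or half-filled fields differently, that difference enters the paired change directly. No concurrent arm is read under the same expectation. The aim in section 2 is to show that food can return without worsening disease, so under-reading of later slides would look like success. Over-reading would look like a flare.

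**Working it through.** **1. What is and is not specified**

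| Question | Where | Answer in the plan |
|---|---|---|
| Who counts, and with what stain? | 5.1.6 | Hospital pathology, H&E |
| How is it counted? | 5.1.7 | Every field at 400X; half-tissue rule; maximum over all specimens |
| Is the reader masked to visit, food step or earlier counts? | 5.1.6, 5.1.7 | Not stated |
| Is blinding addressed? | 7.7.3 | For treatment only |
| Is there a control arm? | 3.2 | No |

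**2. What reader discretion remains**

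Counting every field in every specimen leaves a compliant reader little freedom over how long or where to search. Two judgements are left: whether a cell is an intraepithelial eosinophil, and whether a field is half tissue. A reader tendency that is the same at every visit cancels in the within-patient difference. Only a tendency tied to visit or diet survives.

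**3. What one cell does after food introduction** (bands from 3.1.2, endpoints from 5.3.2)

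| Count | Remission (<6) | Resolution (<15) | Diet band |
|---|---|---|---|
| 5 | yes | yes | <6 |
| 6 | no | yes | 6-15 |
| 15 | no | no | 6-15 |
| 16 | no | no | >15 |

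Moving from 5 to 6 changes remission status and the diet step. Moving from 15 to 16 changes the diet band only, because both counts already fail remission and resolution.

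**4. The plan's own sample size**

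Section 5.6 gives N = 20, alpha 0.05, power 80%, a difference of 11 and an effect size of 0.7. Sidedness is not stated, so two-sided is assumed.
- Normal approximation: (1.96 + 0.84)² / 0.7² ≈ 16.02, rounded up to 17.
- Exact paired t-test: N = 19. At N = 20 the power is 84.4%.

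The stated 20 is reproduced within one patient.

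**5. Sensitivity to an assumed reader shift**

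The documents give no size for a shift, so the values of b below are assumptions. The SD of the change implied by section 5.6 is 11 / 0.7 = 15.7. If later slides are under-read by b cells on average, the standardized effect for a true rise of 11 is (11 − b) / 15.7. With no true change it is b / 15.7 in absolute value. Paired t-test, N = 20, two-sided:

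| b | Power for a true rise of 11 | Rejection rate with no true change |
|---|---|---|
| 0 | 84.4% | 5% |
| 1 | 77.0% | 5.8% |
| 2 | 68.1% | 8.4% |
| 3 | 58.0% | 12.8% |

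Over-reading by the same amount would raise the chance of detecting a rise and give the same last column. The table shows how sensitive the test is. It does not estimate bias in this trial.

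**The case against.** The case against giving this much weight is substantial.

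- **The count is rule-based.** A reader might infer that an unmasked pathologist could search harder on some slides or stop early on others. Section 5.1.7 does not support that for a reader who follows it. This stands, and only cell-level and field-level judgement is left.
- **Section 7.7.3 concerns therapy.** It is tempting to read it as declaring masked outcome reading inapplicable. It does not, and nothing says that the pathologist is told the visit or food step. The plan is silent. This stands, and the point is an omission.
- **The coding in section 5.1.12 is not masking.** That section says "Patient samples will be provided to laboratory and CAG staff using the deidentified study code", which might look like a masking procedure ready to extend to histology. Its purpose is de-identification, and nothing there withholds visit or diet. This stands.
- **The slides belong to clinical care.** Section 7.10.2.2 treats all endoscopies after the first as standard of care, and section 4.2.1 places the next food visit one week (± 3 days) after endoscopy. Labelling the slides with a study code only would obstruct reporting to a named patient. This rules out code-only labels. It does not prevent leaving visit and food step off the requisition.
- **Direction is unknown, and the week 12 read precedes food.** A reader who expects trigger food to cause a flare may over-read, which works against the drug. Knowledge of added food cannot affect the week 12 gating read. Both stand, so the concern is confined to the paired difference and the bands after food introduction.
- **The trial is an exploratory pilot.** That limits the weight of the point but gives no reason to leave a small gap open.

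**Conclusion.** The point holds as a low-cost improvement. Masking of the histology reader to visit and food step is not specified for the primary endpoint, and the only blinding statement answers a different question. The counting rule limits the possible bias without removing it, and with no control arm any visit- or diet-linked shift goes into the paired difference.

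The size and direction are unknown from the documents. What can be stated is that one cell at the 5/6 boundary changes remission status and the diet step, and one cell at the 15/16 boundary changes the diet band only. The power figures rest on an assumed constant shift and on the SD implied by section 5.6. A reader might take them as a forecast of lost power, or as evidence that the counts will be biased. The documents support neither reading.

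Masking would not cure the absence of a control or regression to the mean after patients are selected on a low count at week 12.

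**What to change.** In sections 5.1.7 and 7.7.3, state that:
- visit number, food step and earlier study counts are left off the histology requisition and withheld from the existing pathologist until the peak count is recorded;
- the patient identifiers needed for clinical reporting are kept;
- the count is released as soon as it is recorded, so that diet decisions stay on the planned schedule.

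No second reader, parallel read or end-of-study re-read is needed, and N, alpha and the test do not change. The rule should be in place before slides are read, because a count made with that knowledge cannot be masked afterwards without a re-read.

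The documents give no cost. The judgement here is that it amounts to a change in the requisition and a sentence in each section. The pathologist has less clinical context until the count is filed. Masking may also be incomplete if prior reports are visible in the hospital system, and the protocol should say so.
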